### 8.2.2 Vital signs

- Blood pressure and pulse measurements should be preceded by at least 5 minutes of rest for the participant in a quiet setting without distractions (eg, television, cell phones).
- Vital signs including temperature, pulse rate, respiratory rate, and blood pressure will be measured after 5 minutes rest.
- At Cycle 1 Day 1, vital signs after infusion initiation will be collected more intensively;
  - Vital signs will be measured at Pre-dose, 0.5 ( $\pm 0.25$ ), 1 ( $\pm 0.25$ ), 2 ( $\pm 0.5$ ), 4 ( $\pm 0.5$ ) hours after start of SAR444245 dose.
  - At Investigator's discretion, participants (not in the safety run-in) may have intensive vital sign monitoring (to be measured at Pre-dose, 0.5 ( $\pm 0.25$ ), 1 ( $\pm 0.25$ ), 2 ( $\pm 0.5$ ), 4 ( $\pm 0.5$ ), 8 ( $\pm 0.5$ ), 12 ( $\pm 1$ ), 16 ( $\pm 1$ ), 20 ( $\pm 1$ ), 24 ( $\pm 1$ ) hours after start of SAR444245 dose in an in-patient setting).
- **For the core phase participants:** from Cycle 2 to Cycle 4, study therapy will be administered for all patients in out-patient clinic with vital signs taken prior to dosing, at least 4 to 6 hours after the start of SAR444245 dosing, or for longer periods of time if clinically indicated.
- From Cycle 5 and beyond, vital signs will be collected prior to IMP administration.

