| Directed physical
examination                       |                        | X                             | X          | X                    | X                                     | X         |  | X   |   |  |  | See
Section 8.2.1 |
| Body weight/Height e                        | X                      | X                             |            |                      | X                                     | X         | X  | X   |   |  |  |                                      |
| Vital signs  | X                      | X                             | X          | X                    | X                                     | X         | X  | X   |   |  |  | See
Section 8.2.2 |
| SpO 2                                       | X                      | As clinically indicated       |            |                      |                                       |           |  |   |   |  |  |                                      |

| Evaluation a             | Screening/
baseline | Treatment period b |                         |             |                      |                                       | End of
treatment  | Observation period c               |   |                              | Survival
phone call
follow-up
period d | Notes  |  |
|-------------------------------------|------------------------|-------------------------------|-------------------------|-------------|----------------------|---------------------------------------|--|---|---|------------------------------|--|--|--|
|                                     |                        | Treatment
Cycle 1          |                         |             | Treatment
Cycle 2 | Treatment
Cycle 3
and
beyond |  | EOT Visit                                     | Follow
up Visit 1                          | Follow up
Visit 2         |  |  | Follow
up
Visit 3
and
beyond                               |

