Grade 3/4 TEAEs reported by participants who received SAR444245 24 µg/kg in combination with pembrolizumab (n=6) include Grade 4 lymphocyte count decreased (3 participants, 50.0%), Grade 3 aspartate aminotransferase (AST), alanine aminotransferase (ALT) & gamma-glutamyl transferase (GGT) increased (2 participants each for AST & ALT increased, 33.3%; 1 participant for GGT increased, 16.7%), Grade 3 blood phosphorus decreased & hypophosphatemia (1 participant each, 16.7%), and Grade 3 dyspnea (1 participant, 16.7%).

Grade 3/4 TEAEs reported by participants who received SAR444245 24 µg/kg in combination with cetuximab (n=5) include Grade 3 chills (1 participant, 20.0%) and Grade 3 abdominal pain and vomiting (1 participant for each, 20.0%).

Within the HAMMER study, all together there were 13 patients that experienced any grade of CRS (per CTCAE version 5). Only 1 Grade 4 CRS with Grade 3 hypertension, Grade 2 fever, and Grade 2/3 neurological symptoms (with 24 µg/kg Q3W, 2.6%) is reported among participants who received SAR444245 monotherapy (n=38). From participants who received SAR444245 pembrolizumab combination (n=20), grade 3 CRS (with 16 µg/kg Q3W) is observed in 1 participant (5.0%) with Grade 3 hypotension and Grade 2 fever.

According to literature, prophylactic hydration on the dosing days could mitigate incidence and severity of hypotension as part of CRS. As HAMMER study was not mandating prophylactic hydration before January 2021, the participants who experienced CRS in HAMMER study did not always receive peri-infusion hydration. Based on this learning, hydration and CRS management guidelines have been included in the Phase 2 study protocols.

With respect to PK, SAR444245 exposure increased in an approximately dose-proportional manner in the monotherapy cohorts, and no impact of anti-drug antibody (ADA) on SAR444245 PK could be identified. Also, in the combination cohort, there was no apparent impact of pembrolizumab on the PK of SAR444245.

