- Hepatitis B and C serology will be tested at screening for participants in Germany and Italy (see details and specific instructions in [Section 10.2](#) and [Section 10.8](#)).
- E 17. Known second malignancy either progressing or requiring active treatment within the last 3 years. Participants with basal cell carcinoma of the skin, squamous cell carcinoma of the skin, or carcinoma in situ (eg, breast carcinoma, cervical cancer in situ) that have undergone potentially curative therapy are not excluded.
- E 18. Known severe hypersensitivity ( $\geq$  Grade 3) to or contraindication for the use of any study intervention or components thereof, including premedication to be administered in this study, as well as PEG or any pegylated drug and E. coli-derived protein.
- E 19. Participants with baseline oxygen saturation ( $\text{SpO}_2$ )  $\leq$ 92% (without oxygen therapy).

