## **8.2 SAFETY ASSESSMENTS**

The main anticipated adverse effect for the combination of SAR444245 with other anticancer therapies includes manifestations of cytokine release that can range from fever to hypoxia to hypotension, with or without manifestations that may include any of the organ systems. These mild events occur between around 12 to 18 hours after the first administration and a more intensive monitoring of vital signs is planned during that period. Targeted physical exams and standard laboratory tests will be conducted to monitor potential changes in the main body functions. Measurement of cytokines in plasma are planned at relevant timepoints. White blood cell differential count will be measured to monitor for transient lymphopenia which is commonly observed in the first few days following SAR444245 infusion. Eosinophilia that is surrogate to VLS will also be monitored. IL-5, which is also a marker of VLS, will be included in the PDy cytokine panel. Combining SAR444245 with other anticancer therapies may increase the frequency and severity of immune-related adverse events related to other anticancer therapies. Immune-mediated endocrinopathies involving the thyroid being the most frequent, T3, T4, TSH, and cortisol level will be monitored. When clinically indicated, on-treatment ECG, LVEF and troponin will be assessed and compared to baseline. More details on the safety assessment are provided below. Planned time points for all safety assessments are provided in the SoA.

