**Table 11 - ASTCT CRS consensus grading**

| CRS parameter            | Grade 1           | Grade 2  | Grade 3  | Grade 4  |
|--------------------------|-------------------|--|--|--|
| Fever a       | Temperature ≥38°C | Temperature ≥38°C  | Temperature ≥38°C  | Temperature ≥38°C  |
| With                     |                   |  |  |  |
| Hypotension b | None              | Not requiring vasopressors                               | Requiring a vasopressor with or without vasopressin  | Requiring multiple vasopressors (excluding vasopressin)                              |
| And/or b      |                   |  |  |  |
| Hypoxia                  | None              | Requiring low-flow nasal cannula c or blow-by | Requiring high-flow nasal cannula c , facemask, nonrebreather mask, or Venturi mask | Requiring positive pressure (eg, CPAP, BiPAP, intubation and mechanical ventilation) |

Organ toxicities associated with CRS may be graded according to CTCAE v5.0 but they do not influence CRS grading.

a Fever is defined as temperature ≥38°C not attributable to any other cause. In patients who have CRS then receive antipyretic or anticytokine therapy such as tocilizumab or alternative therapies per site practice in CRS management or steroids, fever is no longer required to grade subsequent CRS severity. In this case, CRS grading is driven by hypotension and/or hypoxia.

b CRS grade is determined by the more severe event: hypotension or hypoxia not attributable to any other cause. For example, a patient with temperature of 39.5° C, hypotension requiring 1 vasopressor, and hypoxia requiring low-flow nasal cannula is classified as grade 3 CRS.

c Low-flow nasal cannula is defined as oxygen delivered at ≤6 L/minute. Low flow also includes blow-by oxygen delivery, sometimes used in pediatrics. High-flow nasal cannula is defined as oxygen delivered at >6 L/minute.

Abbreviations: ASTCT=American Society for Transplantation and Cellular Therapy; BiPAP=Bi-level positive airway pressure CPAP= Continuous Positive Airway Pressure; CRS=Cytokine release syndrome.

Source: (2)

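### Hypoxia helps set the CRS grade, but after screening SpO2 is read only on clinical indication, so that limb is not ascertained uniformly

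*Protocol*

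**What the plan says.** Master protocol Section 8.2.2 lists the components: "Vital signs including temperature, pulse rate, respiratory rate, and blood pressure will be measured after 5 minutes rest". Substudy 01 Section 8.2.2 gives the same list. On Cycle 1 Day 1 both require readings pre-dose and at 0.5, 1, 2 and 4 hours after the start of the SAR444245 dose. Readings from 8 to 24 hours are at the Investigator's discretion for participants outside a safety run-in.

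The Schedule of Activities (Section 1.3, master and Substudy 01) gives SpO2 its own row: a cross at screening, then "As clinically indicated". The screening value is used for eligibility, since exclusion criterion E 19 removes participants at 92% or below.

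Section 8.2 says the main anticipated adverse effect "includes manifestations of cytokine release that can range from fever to hypoxia to hypotension". It places the mild events at around 12 to 18 hours after the first administration and says vital signs will be monitored more intensively in that period.

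Table 11 (Appendix 13) gives the rule: "CRS grade is determined by the more severe event: hypotension or hypoxia not attributable to any other cause". CRS of Grade 2 or higher is an adverse event of special interest (Section 8.3.8), and ASTCT-graded CRS is summarized separately in the safety analysis (Section 9.4.3.5).

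**The concern.** Two parameters raise a CRS event above Grade 1. Blood pressure, which underlies one of them, is read on a fixed schedule. Oxygen saturation, which underlies the other, has no scheduled reading after screening. Whether a febrile, normotensive participant is recognized as hypoxic therefore depends on whether the site decides to apply an oximeter.

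At stake is the comparability of CRS grades across sites and cohorts, chiefly at the boundary between Grades 1 and 2, where the special-interest classification begins. These are descriptive safety summaries in cohorts of about 40, so one or two participants graded differently would be visible in the reported percentage.

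**Working it through.** The concern disputes no stated figure, so most of the check is a comparison of sections.

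**1. Are the two limbs measured alike?**

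| CRS element (Table 11) | Related measurement | On-treatment collection |
|---|---|---|
| Fever | Temperature | Scheduled (8.2.2) |
| Hypotension | Blood pressure | Scheduled (8.2.2) |
| Hypoxia | SpO2 | On indication only (1.3) |

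The vital-sign list opens with a word that need not be exhaustive. The separate Schedule of Activities row settles the matter: SpO2 is not part of the scheduled set.

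**2. Does a missing reading change a grade?** Not directly. Table 11 has no SpO2 cut-off. Hypoxia is graded by support: low-flow nasal cannula or blow-by at Grade 2, high-flow or a mask at Grade 3, and at Grade 4 "Requiring positive pressure (eg, CPAP, BiPAP, intubation and mechanical ventilation". The effect is indirect: if desaturation goes unnoticed, oxygen may not be started and the event may stay at Grade 1.

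**3. Does fever act as a safety net?** In part. Every grade starts from fever: "Fever is defined as temperature ≥38°C not attributable to any other cause". Temperature is scheduled. However, Section 6.1.2.1 gives all participants acetaminophen 30 to 60 minutes before SAR444245 in the first 4 cycles, which may blunt the fever. Footnote a of Table 11 adds that once a participant with CRS has had antipyretic or anticytokine treatment, later grading rests on hypotension and hypoxia alone.

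**4. Do the readings cover the stated window?** Section 8.2 points to about 12 to 18 hours. The last required Cycle 1 Day 1 reading in Section 8.2.2 is at 4 hours (±0.5). For participants outside a run-in, no required reading falls in that window.

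**5. The plan's nearest figure.** Section 9.2 gives the probability of at least one case among 40 at true rates of 1%, 2% and 5%. The formula is 1 − (1 − p)^40, which gives 33.1%, 55.4% and 87.1%, as stated. It takes every event to be ascertained.

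**6. Sensitivity to ascertainment (assumed values, not an estimate).** With detection probability d, replace p by p × d. At p = 5%:

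| d | Expected cases in 40 (40 × p × d) | P(at least 1 seen) |
|---|---|---|
| 100% | 2.0 | 87.1% |
| 90% | 1.8 | 84.2% |
| 75% | 1.5 | 78.3% |
| 50% | 1.0 | 63.7% |

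Neither p nor d for hypoxia-driven CRS is in the documents.

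**7. Weight of one participant.** 1/40 = 2.5 percentage points; 2/40 = 5 points.

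**The case against.** The strongest reply is that SpO2 was placed on indication deliberately, as LVEF and coagulation were, and that the Schedule of Activities and Section 8.2.2 agree with each other. Section 8.2 leaves time points to the schedule. Section 8.2.1 has early signs of CRS prompt a thorough assessment, and the directed examination, which includes the lungs, is scheduled on treatment. Substudy 01 Table 4 asks for close monitoring even at Grade 1. All of this stands, and it limits the concern.

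A reader might infer that hypoxic CRS would be found only by chance. The documents do not support that: measurement follows indication, fever and respiratory rate are screened on schedule, and giving oxygen is an act of care that would normally leave a record.

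A reader might also infer that reported CRS is biased low. Under-grading is the plausible direction, but nothing in the documents demonstrates it.

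Nor can a size be taken from the HAMMER data in Section 4.3:

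- Grade 3 dyspnea at 24 µg/kg (2 of 11 on monotherapy, 1 of 6 with pembrolizumab) pools to 3/17 = 17.6%. Adding the 5 participants on cetuximab, for whom none is listed, gives 3/22 = 13.6%. Either way, dyspnea is neither documented hypoxia nor CRS.
- The 13 CRS cases among 68 patients (19.1%) span several doses and schedules and were graded by CTCAE, not ASTCT.
- The two Grade 3 or 4 CRS cases described mention no hypoxia.

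The objection does not answer the asymmetry between the limbs. The assessment prompted by early CRS signs names no SpO2 reading and presupposes suspicion, and premedication may weaken the fever that would raise it.

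**Conclusion.** The point holds in limited form. After screening, SpO2 is collected only on indication, although hypoxia is a named anticipated effect and one of the two parameters that set the CRS grade. Ascertainment of that limb is therefore not standardized, and CRS may be under-graded around the Grade 2 cut. This assumes that oximetry practice varies between sites and that oxygen is usually started after desaturation or symptoms are noticed; the documents establish neither. The size of any effect is unknown. The primary endpoint is untouched.

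The timing mismatch between Sections 8.2 and 8.2.2 is firmer, because it can be read directly from the text. This assessment covers the master protocol and Substudy 01; the other substudies are not available in full.

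**What to change.** Reconcile Section 8.2, Section 8.2.2 and the SpO2 row of Section 1.3, in the master protocol and in Substudy 01, with Table 11, and state how the hypoxia limb will be ascertained uniformly across sites. Check the other substudies for the same wording.

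One low-cost data-collection route is to record SpO2 at the vital-sign readings already scheduled, including the Cycle 1 Day 1 pre-dose reading. A pre-dose value would also help with the Table 11 requirement that hypoxia not be attributable to another cause. The cost is amendment wording and one e-CRF field, with no new visit or time point. The reported Grade 2 CRS count may rise slightly.

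That route alone would not cover the 12 to 18 hour window. In the same amendment, reconcile the more intensive monitoring that Section 8.2 says is planned with the required readings in Section 8.2.2, which stop at 4 hours. Which monitoring schedule applies is for the sponsor and its clinical team to decide.

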### 8.2.3 Electrocardiograms and left ventricular ejection fraction (LVEF)

- Includes single 12-lead ECG, LVEF and troponin that will be performed at screening and troponin at Cycle 4 Day 1, then, as clinically indicated.
- At Cycle 1 Day 1, at pre-dose and at end of SAR444245 infusion, ECG will be obtained using an ECG machine that automatically calculates the heart rate and measures PR, QRS, QT, and QTcF intervals.
- LVEF evaluation will be done by echocardiography or multigated acquisition (MUGA), and any repeated assessment should be done with the same technology used at screening.
- Additional evaluations such as ECG, LVEF, Holter monitoring, cardiac enzymes (such as troponin) and consultation with a cardiologist should be done when clinically indicated.

- During treatment, or post treatment follow-up: Troponin will be performed at Cycle 4 Day 1. In case of a suspicion of a drug related cardiac event (eg, including signs/symptoms of cardiac disease, ECG and/or echo changes, troponin elevation, etc.), Investigators are encouraged to do ECG, echocardiography and/or cardiac biomarker tests, as medically indicated, including cardiology consultation.

#### 8.2.4 Clinical safety laboratory assessments

- See Appendix 2 ([Section 10.2](#)) for the list of clinical laboratory tests to be performed and the SoA ([Section 1.3](#)) for the timing and frequency.
- The clinical safety laboratory assessments will be done in the local laboratory.
- The Investigator must review the laboratory report, document this review, and record any clinically relevant changes occurring during the study. The laboratory reports must be filed with the source documents. Abnormal laboratory findings associated with the underlying disease are not considered clinically significant, unless judged by the Investigator to be more severe than expected for the participant's condition.
- All laboratory tests with values considered clinically significantly abnormal during participation in the study or within Follow-Up Visit 1 should be repeated until the values return to normal or baseline or are no longer considered clinically significant by the Investigator or Sponsor.
  - If such values do not return to normal/baseline within a period of time judged reasonable by the Investigator, the etiology should be identified, and the Sponsor notified.
  - All protocol-required laboratory tests, as defined in Appendix 2 ([Section 10.2](#)) must be conducted in accordance with the laboratory manual and the SoA.
  - If laboratory values from non-protocol specified laboratory tests performed at the institution's local laboratory require a change in participant management or are considered clinically significant by the Investigator (eg, SAE or AE or dose modification), then the results must be recorded.

#### 8.2.5 Pregnancy testing

- Refer to [Section 5.1](#) Inclusion criteria [I 05](#) for pregnancy testing criteria; the Investigator is responsible for review of medical history, menstrual history, and recent sexual activity to decrease the risk for inclusion of a woman with an early undetected pregnancy
- Women of childbearing potential must have a negative urine pregnancy test result within 72 hours prior to first IMP administration of each cycle, at EOT and every 30 ( $\pm 7$ ) days until 60 days (for Cohort B2) or 120 days (for Cohorts A1, A2 and B1) after the last dose of study treatment. If urine pregnancy results cannot be confirmed as negative, a serum pregnancy test will be required. Pregnancy tests (serum and/or urine tests) should be repeated if required by local guidelines.

### **8.3 ADVERSE EVENTS (AEs), SERIOUS ADVERSE EVENTS (SAEs) AND OTHER SAFETY REPORTING**

The definitions of adverse events (AEs) and serious adverse events (SAEs) can be found in Appendix 3 ([Section 10.3](#)). The definition of AESI is provided in [Section 8.3.8](#). AEs will be reported by the participant (or, when appropriate, by a caregiver, surrogate, or the participant's legally authorized representative if allowed by local regulations).

The Investigator and any qualified designees are responsible for detecting, documenting, and recording events that meet the definition of an AE or SAE and remain responsible for following up AEs that are serious, considered related to the study intervention or study procedures, or that caused the participant to discontinue the study intervention (see [Section 7](#)).

The method of recording, evaluating, and assessing causality of AEs and SAEs and the procedures for completing and transmitting SAE reports are provided in Appendix 3 ([Section 10.3](#)).

#### **8.3.1 Time period and frequency for collecting AE and SAE information**

All AEs, including adverse events of new onset, as well as worsening of baseline signs and symptoms will be collected throughout study period, from the signing of the informed consent form (ICF) until **30 days** following cessation of study treatment.

All SAEs and AESIs will be collected throughout the study period, from the signing of the informed consent form (ICF) until **90 days** following last administration of study treatment.

All SAEs and AESI will be recorded and reported to the Sponsor or designee immediately and under no circumstance should this exceed 24 hours, as indicated in Appendix 3 ([Section 10.3](#)). Investigator will submit any updated SAE data to the Sponsor within 24 hours of it being available.

Investigators are not obligated to actively seek information on AEs or SAEs after conclusion of the study participation. However, if the Investigator learns of any SAE, including a death, at any time after a participant has been discharged from the study, and he/she considers the event to be reasonably related to the study intervention or study participation, the Investigator must promptly notify the Sponsor.

#### **8.3.2 Method of detecting AEs and SAEs**

Care will be taken not to introduce bias when detecting AEs and/or SAEs. Open-ended and non-leading verbal questioning of the participant is the preferred method to inquire about AE occurrences.

